**6.2. Safety and Reactogenicity**

Safety tables will contain proportion for ACWY-TT group (and 95% CI) and proportion for MenPS group (and 95% CI), except where indicated.

**6.2.1. Solicited Local Events**

The analyses of solicited local events will include compilations of the proportion of reactions as well as estimating the difference between vaccine groups in proportions (Table 8).

090177e19088d171\Approved\Approved On: 11-Mar-2019 09:48 (GMT)

**Table 8. Summary of Analyses for Solicited Local Events for Days 0-3 (4 Days) After Booster Vaccination**

Endpoint	Cohort	Statistical Method/Test
Pain, redness, and swelling (all) Grade 3 for pain, >50 mm for redness, >50 mm for swelling Medical advice for pain, redness, and swelling	Booster TVC	2-sided exact 95% CI on each proportion

Abbreviations: ATP = according to protocol; TVC = total vaccinated cohort.

Large injection site reactions after MenACWY-TT booster vaccination will be described in detail.

**6.2.2. Solicited General Events**

The analyses of solicited general events will include compilations of the proportions of events as well as 95% CI from exact test in each group (Table 9).

Occurrence of fever will also be reported per oral temperature Grade 0, 1, 2, and 3 as well as the percentage of subjects with oral temperature reported by cumulative 0.5°C increment.

**Table 9. Summary of Analyses for Solicited General Events Days 0-3 (4 Days) After Booster Vaccination**

Endpoint	Cohort	Statistical Method/Test
Fever, gastrointestinal symptoms, headache, and fatigue (all) Fever $\geq 37.5^{\circ}\text{C}$ , $>38.0^{\circ}\text{C}$ , $>38.5^{\circ}\text{C}$ , $>39.0^{\circ}\text{C}$ , $>39.5^{\circ}\text{C}$ Fever $<37.5^{\circ}\text{C}$ (Grade 0), $\geq 37.5^{\circ}\text{C}$ - $\leq 38.5^{\circ}\text{C}$ (Grade 1), $>38.5^{\circ}\text{C}$ - $\leq 39.5^{\circ}\text{C}$ (Grade 2), and $>39.5^{\circ}\text{C}$ (Grade 3) Fever $>39.5^{\circ}\text{C}$ , Grade 3 for gastrointestinal symptoms, headache, and fatigue Related fever, gastrointestinal symptoms, headache, and fatigue Related fever $>39.5^{\circ}\text{C}$ , related Grade 3 gastrointestinal symptoms, headache, and fatigue Medical advice for fever, gastrointestinal symptoms, headache, and fatigue	Booster TVC	2-sided exact 95% CI on each proportion

Abbreviation: TVC = total vaccinated cohort.

Note: when temperature is measured by the rectal route, the corresponding oral temperature will be derived by subtracting 0.5°C from the temperature recorded.

090177e19088d171\Approved\Approved On: 11-Mar-2019 09:48 (GMT)

**6.2.3. Solicited Events and Unsolicited AEs Combined Days 0-3**

The proportion of subjects with at least 1 event (solicited and unsolicited), with at least 1 local event (solicited event and unsolicited AE), and with at least 1 general event (solicited event and unsolicited AE) during the 4-day (Days 0-3) period following the booster vaccination will be tabulated. Proportions and 2-sided 95% CI's will also be obtained for Grade 3 events. Only the booster TVC cohort will be analyzed (Table 10).

**Table 10. Summary of Solicited Events and Unsolicited AEs, During the 4-Day (Days 0-3) Period After Booster Vaccination**

Endpoint	Cohort	Statistical Method/Test
At least 1 event (solicited event and/or unsolicited AE), or at least 1 local event (solicited local event and/or unsolicited local AE), or at least 1 general event (solicited general event and/or unsolicited general AE),	Booster TVC	2-sided exact 95% CI on each proportion
At least 1 Grade 3 event, at least 1 Grade 3 local event, at least 1 Grade 3 general event	Booster TVC	2-sided exact 95% CI on proportions
At least 1 related event, at least 1 related local event, at least 1 related general event	Booster TVC	2-sided exact 95% CI on proportions

Abbreviations: PT = preferred term; SOC = system order class; TVC = total vaccinated cohort.

**6.2.4. Unsolicited AEs**

AE output will be sorted alphabetically by MedDRA preferred term within SOC. The proportion of subjects with at least one unsolicited AE and the exact 95% CIs will be compiled. Compilations will be performed for AEs, Grade 3 AEs, related AEs, and related and Grade 3 AEs within 31 days after vaccination (Days 0-30). The number and percentage of subjects who experienced SAE and new onset of chronic illness within 31 days following booster vaccination will be tabulated with exact 95% CI. (Table 11).

090177e19088d171\Approved\Approved On: 11-Mar-2019 09:48 (GMT)

**Table 11. Summary of Analyses for Unsolicited AEs Days 0-30 (31 Days) After Booster Vaccination**

Endpoint	Cohort	Statistical Method/Test
All AEs by SOC and PT	Booster TVC	2-sided exact 95% CI on proportions
Grade 3 AEs by SOC and PT	Booster TVC	2-sided exact 95% CI on proportions
Related AEs by SOC and PT	Booster TVC	2-sided exact 95% CI on proportions
Related and Grade 3 AEs by SOC and PT	Booster TVC	2-sided exact 95% CI on proportions
All SAEs by SOC and PT	Booster TVC	2-sided exact 95% CI on proportions
Related SAEs by SOC and PT	Booster TVC	2-sided exact 95% CI on proportions
Fatal SAEs by SOC and PT	Booster TVC	2-sided exact 95% CI on proportions
Related Fatal SAEs by SOC and PT	Booster TVC	2-sided exact 95% CI on proportions
NOCI with PTs in SOC	Booster TVC	2-sided exact 95% CI on proportions

Abbreviations: NOCI = new-onset chronic illness; PT = preferred term; SOC = system organ class; TVC = total vaccinated cohort.

Pregnancies occurring within 31 days (Day 0 to Day 30) after MenACWY-TT booster vaccination will be listed.

**6.2.5. SAEs Reported Before Booster Vaccination**

SAEs related to the primary study MenACWY-TT-036 vaccination and any event related to lack of vaccine efficacy (ie, meningococcal disease) will be compiled. Only SAEs from the last visit in MenACWY-TT-036 or MenACWY-TT-043, whichever is later, until entry in this study will be included. The cohort will be the total cohort at Month 120.

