⁶ Subjects will be questioned at entry of study C0921005 (MENACWY-TT-101 EXT:036 Y10) whether any SAEs occurred since the subject's last visit in MenACWY-TT-036 (109069) study or in the MenACWY- TT-043 EXT:036 Y2, 3, 4, 5 (112148) persistence study.

090177e19088c6d6\Approved\Approved On: 11-Mar-2019 09:45 (GMT)

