10.6.4. Analysis of reactogenicity and safety

The analysis of safety will be done after administration of the booster dose only.

The primary analysis will be performed on the Booster Total Vaccinated cohort and, if more than 5% of the enrolled subjects are eliminated from the Booster ATP cohort for safety a second analysis will be performed on the Booster ATP cohort for safety to support the analyses of the Booster Total Vaccinated cohort.

For each group, after the MenACWY-TT booster vaccination:

The percentage of subjects with at least one local AE (solicited and unsolicited), with at least one general AE (solicited and unsolicited) and with any AE during the 4-day (Days 0-3) solicited follow-up period will be tabulated with exact 95% CI. The same calculations will be performed for symptoms rated as grade 3 and for symptoms related to vaccination.

090177e19088c6d6\Approved\Approved On: 11-Mar-2019 09:45 (GMT)

The percentage of subjects reporting each individual solicited local (any grade, grade 3, medical advice) and general (any grade, grade 3, related, grade 3 and related, medical advice) AE during the 4-day follow-up period (Days 0-3) after vaccination and its exact 95% CI will be tabulated. Occurrence of fever will also be reported per 0.5°C cumulative increment as well as the percentage of subjects with oral temperature >39.5°C. Additionally, large injection site reactions will be described in detail.

The verbatim reports of unsolicited symptoms will be reviewed and the signs and symptoms will be coded according to the Medical Dictionary for Regulatory Activities (MedDRA) for Adverse Reaction Terminology. The percentage of subjects with unsolicited symptoms within 31 days post-booster vaccination (Days 0-30) and its exact 95% CI will be tabulated by group and by MedDRA preferred term. Similar tabulation will be done for grade 3 unsolicited symptoms, for unsolicited symptoms possibly related to vaccination and for grade 3 unsolicited symptoms possibly related to vaccination. The number and percentage of subjects who experienced SAE and new onset of chronic illness within 31 days following booster vaccination will be tabulated with exact 95% CI.

The percentage of subjects using concomitant medication (any medication, any antipyretic/analgesic, any antipyretic/analgesic taken prophylactically, respectively) during the 4-day and 31-day follow-up periods (Days 0-3 and Days 0-30, respectively) after vaccination will be summarized.

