**4.4. Total Cohort at Month 120**

The total cohort at Month 120 will include all vaccinated subjects from the vaccination stage of Study MenACWY-TT-036 who return for the Month 120 follow-up, ie, subjects who were vaccinated in MenACWY-TT-036 and returned for Month 120 visit.

For the analysis of persistence, the total cohort at the Month 120 visit will be further restricted to vaccinated subjects for whom data concerning persistence endpoint measures are available, ie, at least 1 titer at Month 120 visit.

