#### **4.7. Adapted ATP Cohort**

The adapted ATP cohort will denote, for each time point, subjects belonging to the corresponding ATP cohort for immunogenicity (Month 0 and Month 1) or persistence (all other months) for that time point.

The blood sampling intervals are 21 to 48 days for Month 1; 96 to 112 weeks for Month 24; 148 to 164 weeks for Month 36; 200 to 216 weeks for Month 48; 252 to 268 weeks for Month 60; and 494 to 546 weeks for Month 120.

The adapted ATP cohort will be used for the modeling prediction analysis ([Section 5.2.3](#)).

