**5.3.4. Unsolicited SAEs**

The percentage of subjects with SAEs related to primary vaccination and any event related to lack of vaccine efficacy from the subject's last visit in the primary study MenACWY-TT-036 or in the persistence study MenACWY-TT-043 EXT:036 Y2, 3, 4, 5 until entry in Study C0921005 (MenACWY-TT-101 EXT:036 Y10) and the exact 95% CI will be tabulated by vaccine group.

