**Table 12. Summary of SAEs Since Last MenACWY-TT-036 Visit or MenACWY-TT-043 Visit Up to the Booster Vaccination**

Endpoint	Cohort	Statistical Method/Test
SAEs by SOC and PT	Total cohort at Month 120 visit	2-sided exact 95% CI on proportions

Abbreviation: SOC = system organ class.

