**6.4. Baseline and Other Summaries and Analyses**

The descriptive summary for sex, race, and age will be presented by total cohort Month 120, ATP cohort for persistence at Month 120, booster TVC, and booster ATP cohort for immunogenicity populations. Subject’s date of birth, sex, and race information will be from primary study MenACWY-TT-036 or MenACWY-TT-043.

The analyses for study conduct and subject disposition are presented below:

- Number of subjects with booster vaccination, number of subjects completed study, and number of subjects withdrawn in total cohort at Month 120.
- Number of subjects in total cohort at Month 120, number of subjects in ATP cohort for persistence at Month 120, and number of subjects with reason(s) for exclusion from ATP cohort for persistence at Month 120.
- Number of subjects in booster TVC, number of subjects in booster ATP cohort for safety, number of subjects with reason(s) for exclusion from booster ATP cohort for safety, number of subjects in booster ATP cohort for immunogenicity, and number of subjects with reason(s) for exclusion from booster ATP cohort for immunogenicity.
- Number and proportion of subjects returning diary cards in booster TVC.

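### Should the SAP drop the percentage and exact 95% CI for pre-entry related SAEs and vaccine failures because only Month 120 returners are counted, over unequal look-backs?

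*SAP*

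**What the plan says.** SAP 5.3.4 asks for the percentage of subjects with a pre-entry SAE attributed to the primary vaccine, or with a vaccine failure, "and the exact 95% CI will be tabulated by vaccine group". SAP 6.2.5 fixes the period and the denominator: "until entry in this study will be included. The cohort will be the total cohort at Month 120". Table 12, titled "Summary of SAEs Since Last MenACWY-TT-036 Visit or MenACWY-TT-043 Visit Up to the Booster Vaccination", repeats the two-sided exact interval by system organ class and preferred term. SAP 4.4 explains the cohort as "subjects who were vaccinated in MenACWY-TT-036 and returned for Month 120 visit".

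The clock starts at each subject's own last visit in study 036 or 043, whichever is later. Under SAP 2.2.2 the 036 visit counts only for those who never joined 043. The information comes from an interview. Protocol Table 14, footnote 6, says "Subjects will be questioned at entry of study C0921005" about SAEs since that last visit.

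Protocol 10.6.4 treats two periods differently. After the booster, SAEs and new chronic illnesses "within 31 days following booster vaccination will be tabulated with exact 95% CI". For the pre-entry period it promises a detailed retrospective account and mentions no interval.

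**The concern.** Two features make a percentage with a confidence interval look out of place.

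First, being in the denominator depends on the outcome. A subject who died of meningococcal disease or of a related SAE before Month 120 cannot attend, and one harmed by the first vaccine may decline. An exact interval covers sampling error only. Protocol 4.3 also bars some histories, such as Guillain-Barré syndrome, so an affected subject might come back and still not be recorded.

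Second, one subject may contribute about 4 years of exposure and another about 10, with no scaling by time.

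The disposition list in SAP 6.4 starts from those who returned ("number of subjects completed study, and number of subjects withdrawn in total cohort at Month 120"), so the number of non-returners might stay out of sight. The stake would be a reader taking the upper limit as a ten-year safety bound for everyone vaccinated at the site in study 036.

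**Working it through.** **1. Check of the plan's own figures.** Protocol Table 5 allows 520 ± 26 weeks from primary vaccination to Visit 1: 520 − 26 = 494 and 520 + 26 = 546. This matches SAP 4.7, which gives "252 to 268 weeks for Month 60; and 494 to 546 weeks for Month 120". The exact (Clopper-Pearson) method named in SAP 5.1 reproduces Protocol Table 17: for example, 27/135 gives 13.6% to 27.7%, and 41/45 gives 78.8% to 97.5%.

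**2. Length of look-back.** Minimum = 494 minus the latest week of the last visit's window; maximum = 546 minus the earliest. Years = weeks × 7/365.25.

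| Last earlier visit | Window (SAP 4.7) | Look-back, weeks | Years |
|---|---|---|---|
| Month 60 | 252–268 weeks | 226–294 | 4.3–5.6 |
| Month 48 | 200–216 weeks | 278–346 | 5.3–6.6 |
| Month 36 | 148–164 weeks | 330–398 | 6.3–7.6 |
| Month 24 | 96–112 weeks | 382–450 | 7.3–8.6 |
| Month 1 of 036 | 21–48 days | 487–543 | 9.3–10.4 |

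These are windows for the according-to-protocol cohorts and do not bind the total cohort, so real values may fall outside them. The last row assumes that Month 1 was the last 036 visit. The design figure's legend mentions extended safety follow-up of unstated length, which would shorten it.

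**3. What the table would print with no events.** The upper limit is 1 − 0.025^(1/n). For n = 150 it is 2.43%, and for n = 50 it is 7.11% (planned group sizes, Protocol 5.2.1). With one event the intervals are 0.02% to 3.66% and 0.05% to 10.65%.

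**4. The same result per person-time.** The exact Poisson upper limit for zero events is 3.689.
- All look-backs 4.33 years: 3.689/(150 × 4.33) = 0.57 per 100 person-years.
- All look-backs 10.41 years: 3.689/(150 × 10.41) = 0.24 per 100 person-years.

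The ratio, 543/226 = 2.4, compares two extreme cohorts. The documents do not say how many subjects have each look-back, so the actual distortion must be smaller and cannot be stated.

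**5. Selective return.** Suppose subjects with an event return r times as often as the others. A limit p among returners then corresponds to p/(p + r(1 − p)) among all vaccinees. The values of r are assumptions.

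| r | 0/150, p = 2.43% | 0/50, p = 7.11% |
|---|---|---|
| 0.5 | 4.7% | 13.3% |
| 0.75 | 3.2% | 9.3% |
| 1 | 2.4% | 7.1% |
| 1.25 | 2.0% | 5.8% |

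Protocol 1.1 puts case fatality of invasive disease at around 10%. If death were the only barrier to return, r for meningococcal disease would be about 0.9. The first limit would then move to 0.0243/(0.0243 + 0.9 × 0.9757) = 2.7%, and the second to 0.0711/(0.0711 + 0.9 × 0.9289) = 7.8%.

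**6. Who is left out, according to the text.**
- Anaphylaxis to the primary dose would come before a look-back that starts at Month 1 or later. Anaphylaxis to another vaccine is not an SAE related to the primary dose. Neither belongs in this table.
- Meningococcal disease is not itself an exclusion criterion in Protocol 4.3. It removes a subject from the persistence cohort (SAP 4.5), not from the total cohort used here.
- SAP 4.4 defines the total cohort by return, not by eligibility, and SAP 5.4 counts returners separately from those boosted. A returner who is not boosted therefore appears to stay in. Screen failures are not named, so this is a reading, mainly relevant to Guillain-Barré syndrome.
- SAP 5.4 plans counts and proportions, by vaccine group, of subjects returning at Month 120. It names no denominator, but a proportion returning implies a number larger than the returners.

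**The case for a change.** The best argument for a change is that the protocol asked for description, and the SAP added an interval that invites inference. The denominator consists of survivors who came back, time at risk is unequal, and the visible text carries no warning on either point. A listing with look-back lengths would say what is known without suggesting a bound on risk.

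Part of this stands. Fatal pre-entry events cannot appear, and neither 2.4% nor 7.1% is a limit for all 036 vaccinees at the site.

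The rest is weaker. The protocol's wording does not exclude a percentage, and its endpoint in section 10.2 is the occurrence of these events. The SAP introduction reserves the right to modify the protocol's plans. SAP 5.3.3 already lists vaccination-related SAEs and vaccine-failure events, although it does not make the period for that listing clear. A listing alone would have the same survivors and the same gaps. It would also lose the one figure showing that no events among 50 subjects is still compatible with about 7%.

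**Conclusion.** No change to the plan is needed. The percentage and exact interval are valid for the population that Table 12 names, subjects who returned at Month 120. Protocol 10.7 makes all analyses descriptive, and no primary conclusion uses this table. Dropping the interval is a trade-off with no net gain: selection and unequal follow-up lie in the data and would remain in any listing.

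The size depends on the planned 150 and 50 subjects and on zero events, which give upper limits of 2.4% and 7.1%. Look-back of about 4 to 10 years rests on the according-to-protocol windows and on Month 1 being the last 036 visit. The direction of any selection bias is probably towards understatement, but this is not certain, because non-returners leave both numerator and denominator. Its size cannot be derived from the documents. A careful study report would say that only returners are covered, give the look-back range, and set the return counts planned in SAP 5.4 against the number vaccinated. That is ordinary interpretation and alters no result.

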**Table 12. Summary of SAEs Since Last MenACWY-TT-036 Visit or MenACWY-TT-043 Visit Up to the Booster Vaccination**

Endpoint	Cohort	Statistical Method/Test
SAEs by SOC and PT	Total cohort at Month 120 visit	2-sided exact 95% CI on proportions

Abbreviation: SOC = system organ class.

**6.2.6. Concomitant Medications**

The percentage of subjects using concomitant medication (any medication, any antipyretic/analgesic, or any antipyretic/analgesic taken prophylactically) during the 4-day and 31-day follow-up periods (Days 0-3 and Days 0-30, respectively) after booster vaccination will be summarized. The cohort will be the booster TVC. Analyses are summarized in [Table 13](#).

090177e19088d171\Approved\Approved On: 11-Mar-2019 09:48 (GMT)

**Table 13. Summary of Analyses for Concomitant Medications**

Endpoint	Cohort	Statistical Method/Test
Any concomitant medication, any antipyretic/analgesic, any antipyretic/analgesic taken prophylactically Days 0-3	Booster TVC	2-sided exact 95% CI on proportions
Any concomitant medication, any antipyretic/analgesic, any antipyretic/analgesic taken prophylactically Days 0-30	Booster TVC	2-sided exact 95% CI on proportions

Abbreviation: TVC = total vaccinated cohort.

**6.3. Subset Analyses**

Not applicable.

**6.4. Baseline and Other Summaries and Analyses**

The descriptive summary for sex, race, and age will be presented by total cohort Month 120, ATP cohort for persistence at Month 120, booster TVC, and booster ATP cohort for immunogenicity populations. Subject’s date of birth, sex, and race information will be from primary study MenACWY-TT-036 or MenACWY-TT-043.

The analyses for study conduct and subject disposition are presented below:

- Number of subjects with booster vaccination, number of subjects completed study, and number of subjects withdrawn in total cohort at Month 120.
- Number of subjects in total cohort at Month 120, number of subjects in ATP cohort for persistence at Month 120, and number of subjects with reason(s) for exclusion from ATP cohort for persistence at Month 120.
- Number of subjects in booster TVC, number of subjects in booster ATP cohort for safety, number of subjects with reason(s) for exclusion from booster ATP cohort for safety, number of subjects in booster ATP cohort for immunogenicity, and number of subjects with reason(s) for exclusion from booster ATP cohort for immunogenicity.
- Number and proportion of subjects returning diary cards in booster TVC.

**7. INTERIM ANALYSES**

Not applicable.

090177e19088d171\Approved\Approved On: 11-Mar-2019 09:48 (GMT)

